There has been no additional adaptation of the Kitbag itself from the school setting but the support is tailored to the social work setting, focusing on the relationship-based and reflective practice skills of the social workers and their role in leading the shift in practice within their teams.

As mentioned above, we expect that the version of the programme trialled will involve considerably more use of the Kitbag Online than in non-Covid-19 times. We attempt to address the generalisability of the findings in the implementation and process evaluation (please see below).

Logic model

* indicates outcomes that will be measured.

Impact Evaluation

Research questions

Primary research questions

Child outcomes:

- Primary outcome 1: What is the impact of the “Putting the Kitbags to work” programme on the number of **escalations and de-escalations** of eligible children supported by social workers? The comparison is between eligible children supported by social workers in teams randomly allocated to the intervention arm compared with eligible children supported by social workers in teams randomly allocated to the control arm within the intervention period.
- Secondary outcome 1: What is the impact of the “Putting the Kitbags to work” programme on the **behaviour** of eligible children supported by social workers? The comparison is between eligible children supported by social workers in teams randomly allocated to the intervention arm compared with eligible children supported by social workers in teams randomly allocated to the control arm. The outcome will be measured by the total difficulties score of the Strengths and Difficulties Questionnaire. The population will be restricted to children who’ve been looked after continuously for 12 months or more whose SDQ has been assessed from T4 - T12.

Social worker outcomes:

[figure not shown]
- Secondary outcome 2: What is the impact of the “Putting the Kitbags to work” programme on the **self-efficacy** (as measured by the competency subscale of the Work-Related Basic Needs Satisfaction scale) of social workers and family support workers in teams randomly allocated to the intervention arm compared with social workers and family support workers in teams randomly allocated to the control arm? The outcome will be measured at month 6 and month 13 after intervention began.

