We measure this outcome through a decrease in the total difficulties score of the SDQ (the sum of the emotional, peer, behavioral and hyperactivity subscales - all except the prosocial score as scored according to the instructions by the SDQ developers¹⁴). The score ranges from 0 to 40 with a lower score representing better behaviour. Although the individual subscales appear to measure distinct concepts in high total difficulty score populations (like children with a social worker)¹⁵, we use the total difficulty score instead of the individual subscales to reduce measurement error.

For this outcome, the population is restricted to children who've been i) continuously looked after for 12 months or more and ii) who have used Kitbag for four months or more at the time of their SDQ being assessed. i) is the population for whom SDQs are available in administrative datasets and we further restrict this population to ii) to allow for the minimum number of uses of the Kitbag.

Social Worker and Family Support Worker Outcomes

2ii) Social worker / family support worker self efficacy

As represented in the logic model, one of the hypothesised mechanisms is that social workers feel they have the tools to do their job well. We shall measure whether Kitbag improves social workers' self-efficacy through the competence subscale of the Work-Related Basic Needs Satisfaction scale. The competency subscale is a 4-item scale which respondents agree or disagree on a 5-point Likert scale with good reliability (a Cronbach's alpha of .85), and reasonable predictive validity (correlates positively with job satisfaction and vigour, and negatively with exhaustion)¹⁶. The fourth secondary outcome measure is the mean of the responses for the 4 items where "totally disagree" is coded as 1 and "totally agree" is coded as 5 (2iv).

2iii) Stress

As represented in the logic model, one of the hypothesised mechanisms is that social workers feel more valued by the local authority and feel better supported by their team, reducing their stress. Social worker stress will be measured by the 7-item "Stress in General" scale which has good reliability (above 0.7) and good convergent validity (it correlates negatively as expected with job satisfaction and positively with intention to quit)¹⁷. Higher scores represent

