Children are clustered into sibling groups, households (e.g. with other children in foster care) and caseloads (i.e. a group of children have the same social worker) and social worker teams. Because of this clustering, observations within one group (sibling group, household etc) may be more similar with each other on various characteristics compared with observations in other groups violating the assumption of independence. When data is structured in this way, the estimation of the treatment effect remains unbiased but the standard errors may be misspecified, leading to problems with inference. To correct for this, standard errors will be clustered at the level of randomisation, the social worker team level, in line with WWCS statistical guidance. This also accounts for correlations between observations at lower levels of nesting.

Handling non-compliance

If CYP are transferred to another team (e.g. due to a change of status), it is possible that the team to which they are transferred was ineligible for participating in the programme or had a different intervention / comparator group allocation. If a social worker or family support worker changes teams, it is possible that their new team had a different intervention/ comparator allocation. For all our analysis, we will conduct intention to treat analysis where a CYP is considered as treated if they are / were supported by a social worker who is a member of an intervention team at the point they entered the sample (either at randomisation or when their case started), irrespective of their use of Kitbag.

Multiple Comparison Adjustments

We will adjust for multiple comparisons within the secondary outcomes using Hochberg's step-up procedure, as per WWCS statistical guidance.

Regression specification

For social workers, family support workers and foster carer outcomes:

$$Y_{ict13} = \beta_0 + \beta_1 D_c + \beta_{2:4} A_c' + \beta_5 Y_{ict0} + \beta_{6:k+6} X_i' + \beta_{k+6:k+11} M_c' + \epsilon_c$$

Where:

- Y_{ict13} is the dependent variable for individual i , team c at the end of the trial, $t13$. β_0 is the intercept
- D_c is the treatment variable
- A_c is a vector of the local authority fixed effects
- Y_{ict0} is the "pre" outcome of individual i in team c , at their "pre" data collection point, $t0$
- X_i' is an $N \times k$ matrix of characteristics of individual i
- M_c' is an $N \times 5$ matrix of characteristics of team c
- ϵ_c is the error term clustered at the team level c

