Although the total intervention period lasts for 12 months, children and young people enter and leave services throughout the year with an estimated 50% of children and young people at T0 having left services by T13. Because of the extent of the dropoff and because an insight into the impact of the number of sessions Kitbags are used may affect future planning of how Kitbags are used in direct work, we considered it important to analyse the “dosage” of the treatment (where number of months of exposure is taken as a proxy of the number of sessions). Thus for CYPs’ and parents’ / carers’ outcomes (which are collected at the same time as the child’s), we have four possible “dosages” of the treatment: 0 months (control), 0-4 months, 4-8 months and 8-12 months. We test whether the programme affects the duration of the interaction with children’s social care (end date - start date) by regressing the duration of interaction with children’s social care on the independent variables defined in the regression specification above. If the coefficient on the treatment dummy is insignificant, we can be less concerned that the impact of the treatment is determining dosage and we code the treatment variable for the children and young people’s outcomes and the parent / carers’ outcomes as categorical:

- 0: control
- 1: 0-4 months’ treatment
- 2: 4-8 months’ treatment
- 3: 8-12 months’ treatment

The control condition (coded as 0) will be the base category, and so the coefficient on each of the dosages of the treatment can be interpreted as the impact of 0-4 months / 4-8 months / 8-12 months of the treatment on the outcome compared to control.

Dosage will only be tested for child and parent / carer outcomes as the dosage is likely to vary much for them than social workers and family support workers:

$$Y_{ict13} = \beta_0 + \beta_{1:3} D_c' + \beta_{4:6} A_c' + \beta_7 Y_{ict0} + \beta_{7:k+7} X_i' + \epsilon_c$$

Where:

- D_c is a vector of treatment dosages
- And all else is defined as above

Impact on CYP with different levels of CSC involvement

It may be that there is a differential impact for CYP depending on the type / extent of social care involvement (if the child is on a child in need plan or a child protection plan or whether they are looked after). We add an interaction term of treatment and most recent type of CSC intervention at the start of the intervention period:

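### The SDQ outcome section admits only children who have used Kitbag for four months, which control children handled as allocated cannot meet and which contradicts the protocol's own research question and intention-to-treat rule

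*Protocol*

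**What the plan says.** The protocol defines the SDQ population twice.

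- **Research questions, Secondary outcome 1.** Children "looked after continuously for 12 months or more whose SDQ has been assessed from T4 - T12". The comparison is of children in intervention teams "compared with eligible children supported by social workers in teams randomly allocated to the control arm". Kitbag use is not mentioned.
- **Secondary Outcomes, 2i) Emotional and behavioural difficulties.** Children looked after continuously for 12 months or more and, as condition ii), "who have used Kitbag for four months or more at the time of their SDQ being assessed". The reason given is: "we further restrict this population to ii) to allow for the minimum number of uses of the Kitbag".

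Three other places bear on this.

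- **Handling non-compliance:** "For all our analysis, we will conduct intention to treat analysis", with a child counted as treated according to the team at entry, "irrespective of their use of Kitbag".
- **Randomisation:** staff and in-house carers receive a Kitbag through treated teams only.
- **Dosage:** the four exposure levels are "0 months (control), 0-4 months, 4-8 months and 8-12 months".

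**The concern.** Condition ii) depends on what happened after randomisation, and on something that only one arm is meant to have. A set chosen that way is no longer a comparison of randomised groups. Whether Kitbag is used with a child for four months depends on the worker, the carer, the stability of the placement and the child's willingness. Each of these could be related to the SDQ score in its own right, in either direction.

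The outcome matters more than its secondary rank suggests. Since version 1.1 dropped primary data collection from the impact evaluation, the SDQ total score is the only child outcome that measures emotions and behaviour. The protocol itself describes the social care status outcome as further removed from what Kitbag does.

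**Working it through.** The protocol gives no sample size or MDES for the SDQ subset, so there is no figure of its own to reproduce here. The check sets the two definitions against the rest of the protocol.

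**1. Condition ii) applied in both arms.** Control exposure is coded as 0 months, so control children handled as allocated are all removed. Every remaining child has treatment = 1, and the treatment column equals the intercept. In a simulated design with an intercept, treatment and three local authority terms (5 columns), the rank is 5 with all children and 4 after the restriction. The treatment coefficient cannot be estimated.

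**2. Condition ii) applied in the intervention arm only.** Let p be the share of treated children who qualify, and let m1 and m0 be the mean SDQ of treated users and non-users when Kitbag has no effect. By randomisation the expected control mean is p·m1 + (1 − p)·m0. Users minus controls is therefore

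m1 − [p·m1 + (1 − p)·m0] = (1 − p)(m1 − m0).

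The bias is (1 − p) times the user/non-user gap: three quarters of it at p = 0.25 and one quarter at p = 0.75.

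To give a scale, assume a normal propensity to use Kitbag that has correlation ρ with SDQ. The bias in SD units is then ρ·φ(c)/p, with c = Φ⁻¹(1 − p). Neither p nor ρ is in the protocol; the ranges are assumptions.

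| p | φ(c)/p | ρ = 0.1 | ρ = 0.2 | ρ = 0.3 |
|---|---|---|---|---|
| 0.25 | 1.271 | 0.127 | 0.254 | 0.381 |
| 0.50 | 0.798 | 0.080 | 0.160 | 0.239 |
| 0.75 | 0.424 | 0.042 | 0.085 | 0.127 |

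These values are before covariate adjustment. The only yardstick in the protocol is the MDES of 0.127 SD, which was computed for 9000 children in 60 teams and not for this subset.

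**3. The research question's definition.** Time in care and a calendar window apply equally to both arms, so the randomised comparison is kept.

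**4. Do the two definitions coincide within the intervention arm?** The section on previous outcome measures sets T0 = April 2021, T6 = October 2021 and T13 = May 2022, so T4 = August 2021, T5 = September 2021 and T12 = April 2022. The timeline puts launch at 10 May 2021. Four months later is 10 September 2021, in T5. An August SDQ falls about 2.7 to 3.7 months after launch (83 to 113 days), so it meets the research question's window but not the four months in 2i).

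**5. Could condition ii) be applied at all?** The sources described do not give Kitbag use for each child. The child data are administrative records of social care involvement. Kitbag Online log-ins are anonymous, at most five recording sheets per local authority are reviewed, and the staff survey asks about frequency of use with an assumed 10% response rate.

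**The case against.** The strongest reply is that condition ii) is loose wording for elapsed time. Elsewhere the protocol uses months as a stand-in for sessions: in the team eligibility rule, the December 2021 cut-off and the dosage analysis. On that reading the T4 to T12 window is simply condition ii) expressed in dates. The intention-to-treat statement covers every analysis, and child-level use could hardly be measured anyway, so analysts would probably fall back on the dates.

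Much of this stands. A reader might infer that the randomised comparison is already lost. The protocol does not support that: an arm-neutral population and an explicit intention-to-treat rule are both in it, and the comparison is lost only if the text of 2i) is followed. But the reply does not settle which text governs. The analysis plan refers the reader to the outcomes section for the definitions, and even time exposed is 0 months for controls in the protocol's own coding.

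Three other strong readings also go too far.

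- **That no control child could ever qualify.** The protocol allows for transfers to teams with the other allocation and for some cross-team contamination. Such children would be few and selected, and would not restore the comparison.
- **That the bias is the whole user/non-user gap, with no correction possible.** It is (1 − p) of the gap, and adjustment for prior SDQ (where available), care type, age and disability would remove some of it. No listed covariate measures propensity to use Kitbag.
- **That the window generally fails because late entrants could be assessed soon after joining.** A case first opened in November 2021 cannot reach 12 months in care by T12 (April 2022). Qualifying children must have been in care by about April 2021, so only those who join an eligible team later could be affected.

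**Conclusion.** The point holds as a contradiction that has to be resolved before analysis. Section 2i) selects on receipt of the intervention; the research question and the intention-to-treat rule do not; and the protocol gives no order of precedence.

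If 2i) is followed in both arms, the effect cannot be estimated. If it is applied to the intervention arm only, the bias is (1 − p) times the user/non-user gap. That is roughly 0.04 to 0.38 SD before adjustment, assuming that 25% to 75% of treated children qualify and that propensity to use has a correlation of 0.1 to 0.3 with SDQ. Those inputs are illustrative, and the sign could go either way.

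The mismatch between T4 and four months from launch is minor. It affects both arms equally and does not threaten validity, but the two sections should agree.

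**What to change.** Delete the Kitbag-use condition from 2i) and put one rule, in the same words, there and under Secondary outcome 1. The population is children continuously looked after for 12 months or more, with an SDQ dated at least four months after launch (or after the child's entry to an eligible team, if later) and within the evaluation period, regardless of Kitbag use. Analyse by the allocation of the child's team at entry to the sample. Any question about longer or heavier use belongs in the exploratory dosage analysis.

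The rule needs only dates and team allocation. The cost has two parts.

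- SDQs dated 1 August to 9 September 2021 are dropped in both arms. That is 40 of the 273 days from August 2021 to April 2022, about 15% of records if assessments are spread evenly (an assumption).
- Including treated children with little or no use dilutes the estimated effect somewhat, as intention to treat requires.

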¹² Lundh, L.G., Wangby-Lundh, M., & Bjarehed, J. (2008). Self reported emotional and behavioral problems in Swedish 14 to 15-year-old adolescents: A study with the self-report version of the Strengths and Difficulties Questionnaire. *Scandinavian Journal of Psychology*, 49, 523–532.

¹³ <https://youthinmind.com/products-and-services/sdq/>

¹⁴ Scoring the Strengths & Difficulties Questionnaire for age 4-17. (2014).

<https://www.ehcap.co.uk/content/sites/ehcap/uploads/NewsDocuments/236/SDQEnglishUK4-17scoring-1.PDF#page=4>

¹⁵ Goodman A, Lamping DL, Ploubidis GB. When to use broader internalising and externalising subscales instead of the hypothesised five subscales on the Strengths and Difficulties Questionnaire (SDQ): data from British parents, teachers and children. *J Abnorm Child Psychol*. 2010 Nov;38(8):1179-91. doi: 10.1007/s10802-010-9434-x. PMID: 20623175.

¹⁶ Van den Broeck, A., Vansteenkiste, M., De Witte, H., Soenens, B., & Lens, W. (2010). Capturing autonomy, competence, and relatedness at work: Construction and initial validation of the Work-related Basic Need Satisfaction scale. *Journal of Occupational and Organizational Psychology*, 83(4), 981-1002.

¹⁷ Stanton, J. M., Balzer, W. K., Smith, P. C., Parra, L. F., & Ironson, G. (2001). A General Measure of Work Stress: The Stress in General Scale. *Educational and Psychological Measurement*, 61(5), 866–888. <https://doi.org/10.1177/00131640121971455>

more stress. The sixth secondary outcome measure is the mean of the responses for the 8 items¹⁸ where “no” is coded as 0, “?” is coded as 1.5 and “yes” is coded as 3 (2vi)¹⁹.

2iv) Days attended

The hypothesised lower stress may lead to fewer sick days of social workers. We measure this over the entire intervention period from T1 to T13. Instead of measuring the number of sick-days, we will instead measure the number of ‘days attended’ in work. This allows us to include social workers who leave their posts over the course of the trial - these individuals will be classified as absent every day after they leave. Excluding these participants from the absence analysis would risk biasing the results, as individuals’ likelihood to leave is correlated with their rate of sickness absence. The number of days not attended may include holidays and parental leave in addition to sickness absence. If possible, we will control for the number of days of holiday and parental leave.

Foster and kinship Carer Outcomes

2v) Self-efficacy

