- for social workers and family support workers: the social worker or family support worker was a member of a team assigned to the intervention at point of randomisation and 0 else;
- for foster / kinship carers: the carer cares for a child or young person whose case is held at the point the foster carer enters the sample, by a social worker who is a member of a team assigned to the intervention at point of randomisation and 0 otherwise.

Although there is some turnover of social workers, family support workers and foster carers, about 80% of those at T0 (April 2021) will still be working with the local authority at T13 (May 2022), and so 80% will have received the full 12 months of the intervention. Binarising the treatment seems a reasonable proxy in this case.

For the outcomes relating to children, treatment is coded as a binary variable. When children enter the sample, at either the point of randomisation, or the point they become eligible (e.g. their case opens and meets other criteria) they will be allocated to treatment if the team of their allocated social worker was randomised to treatment.

Covariates

Including control variables increases the precision of the estimate. In each regression, we control for a number of relevant covariates. We outline different categories of covariates below.

Site effects

We include site fixed effects but not site-treatment interaction terms.

Previous outcome measures

We control for the previous measurements of the outcome variable where data is available. For the survey-based measures for social workers, family support workers and foster carers, the same measures will be asked at T6 (October 2021) and T13 (May 2022), and for administrative data we expect previous values to be available. For the outcomes of the CYP and parents / carers (including kinship carers), the previous measure of the outcome will be at T0 (April 2021) or when they entered services if they entered services after T0 (April 2021).

Other covariates

For CYP outcomes (primary outcome i) and secondary outcome i)), we include the following vector of individual-level covariates:

- gender (coded as male, female, or other/missing)
- age group (4-11, 12-17, 18 years, or missing with 4-11 as the reference category)
- ethnicity (Asian / Asian British, Black / African / Caribbean / Black British, Mixed / Multiple ethnic groups, Other ethnic group, White, missing; with the majority group as the reference category)

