Pseudonymised administrative data on interactions with children's social care (CIN plans, CPP, CLA and case closure) will be requested from local authorities. Consent for the sharing of this data will not be explicitly sought from families. This is because we consider the risk to participants arising from the sharing and processing of this data for the purpose of the evaluation to be very low, and the benefit to accessing the data for all eligible participants to be high. The risk that the eligible participants are identified is very low, and the risk of a data breach will be carefully managed so that it remains low. The benefit of accessing the data for all eligible participants is that we maintain statistical power and reduce the risk of selection bias into the sample, allowing for better - unbiased and more precise - estimates of the treatment effect, making the evaluation much more useful to decision-makers. Having said this, participants will be able to withdraw their consent for their data to be processed for the evaluation if they so choose to via a form on the WWCS website. Please see the Data Protection section below for more details on the data governance of this.

Social workers and family support workers

Pseudonymised administrative data on the sickness absence of social workers and family support workers will be requested from local authorities. Consent for the sharing of this data will not be explicitly sought from social workers for the same reasoning as above.

Summary statistics about access to Kitbag Online will be requested from IFF. Given that the social worker participants will not have accessed the website before, it may be possible to add consent to share for purposes of the evaluation into the terms of use. We are currently investigating this with the delivery partners.

Implementation and process evaluation

Focus group discussions and interviews

Focus group discussion and Interview participants will be sent an information sheet in advance of the interview. Before the interview commences, the researcher will ask the participant if they have read and understood the information sheet, and whether they have any questions. The researcher will then elicit consent for participation and for the interview to be recorded. When eliciting consent for participation in interviews, researchers will make clear the limits of confidentiality (See Section D for further information).

Observation

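### Controlling for holiday taken during the trial can remove a substantial part of any Kitbag effect on days attended that works through staff leaving

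*Protocol*

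**What the plan says.** The research question for secondary outcome 4 concerns sick days. Protocol section 2iv) replaces that measure: "we will instead measure the number of ‘days attended’ in work". The window is fixed: "We measure this over the entire intervention period from T1 to T13". Leavers stay in the analysis, and "these individuals will be classified as absent every day after they leave". The reason given is that excluding them could bias the result, because their "likelihood to leave is correlated with their rate of sickness absence".

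The section then acknowledges that the new measure picks up other absence: "The number of days not attended may include holidays and parental leave in addition to sickness absence". Its answer is the sentence at issue: "If possible, we will control for the number of days of holiday and parental leave".

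The Analysis plan makes the model OLS and reads the treatment coefficient as the impact. Its covariate list for social workers and family support workers does not mention leave, so 2iv) is the only place where this adjustment is specified. It does not say whether holiday and parental leave form one term or two. On turnover, the plan expects that "about 80% of those at T0 (April 2021) will still be working with the local authority at T13 (May 2022"). The Cost evaluation (Valuing benefits and disbenefits) takes the treatment coefficient from this regression as sick days averted.

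**The concern.** The outcome counts a day after exit as a day lost, so a difference between arms in leaving is part of the treatment effect by construction. Holiday taken in the same window happens after randomisation and stops at exit. Where entitlements are similar, people differ in holiday taken largely because some left early. A regression that compares staff with equal holiday therefore comes close to comparing staff with equal time in post, and conditions away part of any effect on leaving.

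The adjustment may also miss its own aim. Netting leave out of attendance needs a coefficient near -1, since one more day of leave costs one attended day. Without time in post in the model, the holiday coefficient can be strongly positive, because more holiday signals a longer stay.

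At stake is the estimate for one outcome in the Hochberg-adjusted secondary family, and the benefit figure derived from it.

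**Working it through.** The protocol states no effect size or variance for days attended, so there is no figure to reproduce. The check asks how much of an effect through leaving survives the adjustment.

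**Inputs.** From the protocol: OLS, leavers scored absent after exit, about 80% retention. Assumed: W = 282 working days; leaving 20% in control and 15% in intervention; leaving dates uniform; 30 holiday days a year accrued pro rata, so a = 30/282 = 0.106 per day in post; holiday SD of 2, 5 or 8 days among full-year staff, with variance proportional to time in post; sickness 5% of available days in both arms.

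**1. Unadjusted effect.** Each leaver loses 282/2 = 141 days on average.
- Difference in time in post: 0.05 × 141 = 7.05 days.
- Difference in holiday taken: 0.106 × 7.05 = 0.75 days.
- Difference in days attended: 0.95 × (7.05 - 0.75) = 6.0 days.

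**2. Spread of time in post** at average leaving of 17.5%.
- Mean: 282 × (1 - 0.175/2) = 257.3.
- Mean square: 282² × (0.825 + 0.175/3) = 70,246.
- Variance: 70,246 - 257.3² ≈ 4,030, so the SD is about 63 days.
- Holiday variance due to time in post: 0.106² × 4,030 ≈ 45.6.

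**3. Holiday as its own covariate.** Let r = 45.6 / (45.6 + 0.9125 × SD²), where 0.9125 is the mean fraction of the year in post. The holiday coefficient is about 0.95 × (r/a - 1), and the adjusted effect is 6.0 minus that coefficient × 0.75.

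| Holiday SD | r | Holiday coefficient | Adjusted effect | Removed |
|---|---|---|---|---|
| 2 | 0.93 | +7.3 | 0.5 | 92% |
| 5 | 0.67 | +5.0 | 2.2 | 63% |
| 8 | 0.44 | +3.0 | 3.8 | 37% |

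Simulation of this set-up with parental leave added as a second term gave 0.5, 2.1 and 3.6 days, that is 92%, 65% and 40% removed. A separate simulation (260 days, retention 77.5% v 82.5%, accrual 0.12 per day) removed 93% at SD 2, 64 to 67% at SD 5, about half at SD 7 and 26 to 30% at SD 10.

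**4. Holiday and parental leave as one sum.** With 4% taking parental leave, simulation removed essentially nothing in the 282-day set-up and 2 to 3% in the 260-day one (SD up to 5); with 2% on parental leave, about 10% and 12 to 14%. Parental leave dominates the sum, and at 4% its coefficient was about +0.1, far from -1. If nobody takes parental leave, the sum is just holiday and step 3 applies.

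**5. Parental leave as a separate term.** Its coefficient was about -0.9, close to what a leave correction needs.

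**6. Effect on sickness only, equal leaving.** In the 260-day set-up, 4.1 days unadjusted became 3.9 adjusted with two terms. There is almost no distortion.

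**7. Leave credited in the outcome.** The effect through leaving is kept: 7.05 days less 5% sickness on the 6.3 extra available days gives about 6.7. Simulation gave 6.5 to 7.

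**The case against.** A reader might infer that the adjustment removes most of a retention effect which the outcome was designed to capture. The protocol does not support that.

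- **Most** needs holiday as its own term, or almost no parental leave, and a holiday SD below about 7 days. The text leaves one term or two open, and a single combined count is a fair reading.
- **Designed to capture** is not stated. Leavers are kept to avoid bias from excluding them. Retention is not a named outcome, and the hypothesis is about sick days. A sickness-only effect comes through nearly intact.
- The five-point difference in leaving is an assumption. With 600 staff (also assumed), the 6-day effect has a standard error of about 4.7 days before clustering, so t = 6/4.7 ≈ 1.3. Because the Cost evaluation counts only outcomes significant at 5%, such an effect would often not reach it.
- The sentence is conditional on data. The consent section on administrative data mentions only sickness: "Pseudonymised administrative data on the sickness absence of social workers and family support workers will be requested from local authorities". Entitlement fixed at baseline is not excluded and would be harmless.

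These points limit the size and severity but do not rescue the sentence. It follows directly on days not attended in the T1 to T13 window, so leave taken in that window is the natural reading, and days of parental leave are not naturally a baseline entitlement. The summed version is harmless only where it also fails to net leave out. Making the adjustment depend on which data arrive also lets data supply decide which effect is estimated.

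**Conclusion.** The point holds in limited form. As naturally read, the plan conditions on a post-randomisation variable that stops at exit, while scoring days after exit as absence. With holiday as a separate covariate, this can remove roughly 90%, 60 to 65% or 35 to 40% of an effect through leaving, at holiday SDs of 2, 5 and 8 days. These shares rest on assumed leaving rates, accrual, holiday spread and uniform leaving dates; only the roughly 80% retention is documented. With one summed term and a few percent on parental leave, little is removed and leave is not corrected for. Parental leave as a separate term behaves about as intended.

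It would go too far to conclude that the estimate will be biased towards no effect: that requires Kitbag to change leaving, and it requires holiday to enter in a form the text does not fix. This should be corrected for one secondary outcome and its use in the cost evaluation. The primary outcome is unaffected.

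**What to change.** Replace the sentence in 2iv) with a rule that leave taken during the trial is not a covariate and is credited in the outcome instead:

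Y = days attended + holiday days taken + parental leave days taken = contracted days T1 to T13 - sickness days - contracted days after exit.

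Holiday and parental leave are then neither absence nor adjusters, leavers still count as absent after exit, and an effect through leaving is kept. Request contracted days and leaving dates together with the sickness data. Where a local authority cannot supply leave or contract data, analyse days attended without a leave adjustment. Only leave entitlement, or leave taken before T0, may be a covariate.

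The cost is one sentence and one or two extra HR fields, with somewhat more noise where those fields are unavailable.
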